11.0 STATISTICAL CONSIDERATIONS

Statistical Power: In this non-randomized trial, the primary surrogate marker will be Ki-67. Individuals who exhibit at least 40% reduction in Ki-67 from baseline will be categorized as responders. For p = probability of response, the null hypothesis is specified as p_0 , and the alternative as p_1 . Our null hypothesis is that after 4 weeks of therapy, no more than 5% of the subjects will exhibit at least 40% decrease in Ki-67 levels. Table 1 gives the number of subjects necessary to detect differences of 25% to 45% from the null proportion of 5%, using the binomial test with a significance level of 0.05. Thus, for 90% power, 24 evaluable subjects are necessary to detect a difference of 25% from the null. Because of the necessity of working with patients with a small tumor size all patients accrued may not be evaluable. We anticipate a non-evaluability rate of 50% as quoted by experienced investigators. Hence, we will accrue 42 patients on this trial.

In this non-randomized trial, the primary surrogate marker will be Ki-67 level.

Table 1. Number of subjects, $p_0 = 0.05$

p_1	80% Power	90% Power
0.30	18	24
0.35	12	18
0.40	10	12
0.45	9	10
0.50	5	9

All of the quantitative results generated by IHC (percentage of eg. Ki67) will be given as their arithmetic mean levels. The comparison of changes in proliferation markers and receptor levels between responders and nonresponders will be performed using the Mann-Whitney U test.

The Primary outcome is response to treatment. For each participant, the post-treatment level of Ki-67 will be compared to the pre-treatment level of ki-67. If at least a 40%

decrease from the pretreatment level achieved, the participant will be classified as a responder. The proportion responding and the 95% confidence interval for this proportion will be calculated. The 2-sided binomial test with $\alpha = 0.05$ will be performed to test $p_0 = 0.05$ vs. $p_0 \neq 0.05$.

The secondary aims of the study are to evaluate change from baseline in the MRI parameters, vascular volume (V_b) and K_2 . The distribution in changes from baseline in tumor estrogen, V_b , and K_2 will be examined using probability plots. The Kolmogorov-Smirnov goodness-of-fit test for normality will be performed. If indicated, normalizing transformations will be applied. Ninety-five percent confidence intervals for mean change from baseline and mean percent change from baseline will be computed.

Immunohistochemistry of p53, TSP-1, CD31, CD105, and VEGF will be analyzed as markers of angiogenesis. We expect to observe a greater anti-angiogenic effect in the tumor with the higher angiogenic activity (i.e. with a higher CD31 and CD106 vessel density or a higher VEGF before treatment). According to pre-treatment CD31, CD105, or VEGF, the tumors will be categorized into 3 groups with high, medium, and low angiogenic activities. Normalizing transformations for each variable will be considered. We will evaluate these parameters using analysis of variance to test for reduction from baseline, followed by the sequentially rejective Bonferroni procedure for multiple comparisons to maintain an overall significance level of 0.05. Changes in p53 and TSP-1 will be evaluated similarly.

Data Safety and Monitoring Committee (DSMB)

This study will be monitored throughout accrual and follow-up periods by the UCI Data Safety and Monitoring Board (DSMB). There is a single DSMB to monitor all UCI therapeutic trials. This committee is responsible for reviewing interim analyses prepared by the study statistician and for recommending whether the study needs to be modified or terminated based on these analyses. This committee also determines when the study results will be submitted for publication or otherwise released to the public. It will review any major modifications to the study proposed by the Study Committee. The Study Committee is responsible for monitoring the data from the study for toxicity, feasibility, and accrual. The study committee also initiates minor changes in the study such as clarification of eligibility criteria.

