1.0 OBJECTIVE

- 1.1 To assess the efficacy in terms of reduction in Ki-67(as a surrogate endpoint to breast cancer risk reduction) in patients treated with anastrozole.
- 1.2 To measure the histopathological response and correlate the degree of histopathological response with the degree of Ki-67 response.
- 1.3 To compare pretreatment vascular density with post treatment vascular density using MRI
- 1.4 To compare pretreatment markers of angiogenesis with post treatment marker of angiogenesis.
- 1.5 To correlate MR imaging response to markers of angiogenesis response.
- 1.6 To correlate ER, Ki-67, angiogenesis markers and MRI response to histopathological changes

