The successful completion of specific aims 1 and 2 will allow us to determine whether there is reduction of Ki-67 in response to 4 weeks of anastrozole and what percentage of patients show reversibility of carcinogenesis process by histopathological evaluation of lumpectomy/mastectomy specimen. Specific aim 3 and 4 will define angiogenesis response to hormonal manipulation as reflected by MRI and IHC. In this manner the best surrogate endpoint will be established to be used in future trials of hormonal agents, angiogenesis inhibitor, biological response modifiers etc. This will further allow a fast screening of chemopreventive agents by using the intermediate endpoint of breast cancer risk reduction instead of using the breast cancer risk reduction as the endpoint.

Breast cancer is one of the most common cancers seriously afflicting women in the United States. Of the one million incident cases that are reported annually there are approximately 193,000 new cases of breast cancer (Greenlee, 2001). Although significant advances have been made both in early detection and treatment of breast cancer, the impact of these on reduction in mortality has been modest (Peta, 2000). Furthermore, despite data implicating diet and other environmental risk factors, no lifestyle changes have yet been shown to significantly reduce the risk of breast cancer. Therefore, chemoprevention of breast cancer is a worthwhile approach to reduce the incidence of breast cancer.

There is every reason to believe that a detailed understanding of the initiation, promotion and growth of breast cancer will ultimately provide a rational strategy upon which to base prevention strategies. While the pathways of breast cancer development are not yet fully understood, a role for estrogens in breast cancer etiology has been well established (Hulka, 1995; Kreiger, 1999).

While many pathways are involved in breast cancer etiology, including loss of tumor suppressor function by p53 or BRCA1 and gain of HER2 oncogene expression, their exact role in an individual patient's cancer development may vary (Marquis, 1995; Boggio, 1998).

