Angiogenesis plays a fundamental role in tumor growth and metastasis. Investigations by Teruyama et al. and Mastuyugin et al. have established a relationship between VEGF expression and p450 aromatase activity (Teruyama, 2001; Mastuyugin, 2002). We have previously shown that dynamic contrast enhanced MRI in conjunction with compartmental modeling may be used to assess the angiogenic status of tumors while enabling the study of both breasts (Su, 2002). Additionally, image based measurement techniques do not suffer from the errors due to tissue heterogeneity and use of limited spatial sampling imposed in methods such as histology. Furthermore, MRI based parameters that describe breast physiology have been found to correlate well with immunohistochemically measured angiogenesis markers (Su, 1995; Su, 1994; Su, 1996). *Thus, dynamic contrast enhanced MRI will be used as a secondary surrogate marker in the proposed study.*

Methodology to test the hypothesis: Core biopsies will be obtained from patients whose mammographic findings are suspicious for DCIS. Patient will undergo MRI study prior the biopsy. At the time of biopsy, a portion of the tissue retrieved will be sent in formalin for histopathological examination for Ki-67, ER, PR and angiogenesis markers evaluation.

1 mg of anastrozole administered orally daily for 4 weeks after the diagnosis of DCIS/invasive breast cancer. The reason for using a 4-week regimen is that this is the average time between diagnostic biopsy and definitive lumpectomy or mastectomy.

Patients will undergo MRI at baseline before therapy and then again after anastrozole treatment that will be followed immediately by definitive surgical procedure, i.e. lumpectomy or mastectomy. Lumpectomy/mastectomy specimen will be again evaluated for the level of tumor

Ki-67 decline and the level of angiogenesis markers. The specimen will be subjected to the routine histopathological, and ER and PR evaluation. Histopathological changes pre and post anastrozole will be evaluated in an exploratory analysis.

Detailed Methodology

1. **Quantification of Ki-67 as a Primary Marker to Monitor Response to Chemoprevention by Aromatase Inhibitor Anastrozole**

Measurement of Ki-67 Levels.

[figure not shown]
Measurement of **Ki67** will be performed with the MIB1 mouse monoclonal antibody. To ensure acceptable precision, quantitation of Ki67 will involve the counting of 1000 cells.

Other Tissue Biomarkers.

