10.0 CRITERIA FOR EVALUATION AND ENDPOINT DEFINITIONS

10.1 Absolute percent Ki-67 change pre anastrozole and post anastrozole as well as percentage of patients achieving less Ki-67 less than 10%

10.2 Histopathological response.

A complete response (CR) indicating the disappearance of the primary tumour; a partial response (PR) indicating a reduction of $\geq 50\%$; stable disease (SD) indicating a reduction of $< 50\%$ or increase in size of $< 25\%$; progressive disease (PD) indicating an increase in size of $\geq 25\%$.

The pathological CR will be evaluated by tumour excision and axillary node resection (in case of invasive breast cancer only). Two grading classifications will be utilised to evaluate the tumour response after chemotherapy. In the Chevallier classification, the absence of invasive tumour cells, or persistence of *in situ* disease, and negative axillary lymph nodes define a pathological CR. In the Sataloff classification, we have similar criteria for a pathological CR, but also observe the persistence of small clusters of widely dispersed cells in these cases.

We will correlate patients with degree of drop of Ki-67 with degree of pathological response

10.3 MRI is obtained at the base line and 4 weeks after anastrozole.

MRI characteristics pre and post anastrozole

10.4 IHC determination of markers of angiogenesis and ER, PR and pre anastrozole and post anastrozole expressed as IHC scores and percentage.

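### Section 11 tests Ki-67 only as a responder share: the continuous change listed in Section 10.1 has no stated confidence interval or test against no change, and the planned Mann-Whitney comparison cannot supply one

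*Combined protocol and SAP*

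**What the plan says.** Objective 1.1 is "To assess the efficacy in terms of reduction in Ki-67", and the Specific Aims in Section 2.0 say that Aims 1 and 2 will determine "whether there is reduction of Ki-67 in response to 4 weeks of anastrozole". Neither ties the question to a cut-off.

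Section 10.1 lists as Ki-67 criteria "Absolute percent Ki-67 change pre anastrozole and post anastrozole as well as percentage of patients achieving less Ki-67 less than 10" per cent. The 40% responder is not in that list.

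Section 11.0 classes a patient as a responder if Ki-67 falls by at least 40%. It gives a 95% interval for the responder share and a two-sided binomial test at 0.05 of the null that "no more than 5% of the subjects will exhibit at least 40% decrease in Ki-67 levels". For IHC results as quantities, including Ki-67, it provides arithmetic means and states that the "comparison of changes in proliferation markers and receptor levels between responders and nonresponders will be performed using the Mann-Whitney U test". Objectives 1.2 and 1.6, the Specific Aims and Section 10.2 add correlations of Ki-67 with pathological response, MRI and angiogenesis markers.

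For other markers Section 11.0 goes further. In the paragraph on tumor estrogen and the MRI parameters, "Ninety-five percent confidence intervals for mean change from baseline and mean percent change from baseline will be computed". The angiogenesis markers are evaluated "using analysis of variance to test for reduction from baseline". Neither sentence names Ki-67.

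**The concern.** The primary marker is analysed less fully, as a quantity, than the secondary and exploratory ones. The responder share says how many patients cross a 40% line. It does not say how large the typical fall is, and one share is compatible with very different falls. A reader who wants the size of the Ki-67 change, which the objective and Section 10.1 both point to, would get mean levels without an interval.

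The one planned test that takes Ki-67 change as its outcome looks as if it fills this gap, but it does not. If the groups are formed by the Ki-67 fall, a difference in Ki-67 fall between them is built in. A small p-value from it could be reported as evidence of effect when it carries none.

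A smaller matter: the share with Ki-67 below 10% can, as worded, count patients who were already below 10% before treatment.

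**Working it through.** **1. The plan's own figure.** Inputs from Section 11.0: null 0.05, alternative 0.30, 24 evaluable patients, 90% power. Exact binomial at n = 24:
- Reject at 5 or more (equal tails, 0.025 each): size 0.0060, power 88.9%.
- Reject at 4 or more (one-sided 0.05, or the minimum-likelihood two-sided test): size 0.0298, power 95.8%.

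So 24 is reasonable. Accrual of 42 with 50% evaluable gives 42 × 0.5 = 21. There the rule is 4 or more, with size 0.0189 and power 91.4%. I use 21 below, and 24 where it matters. (24 evaluable at 50% would need 48; that is a separate point.)

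**2. What each measure gets.**

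| Measure | Interval | Test against no change or a null |
|---|---|---|
| Ki-67 responder share | 95% CI | Binomial against 5% |
| Ki-67 change | None stated | None stated |
| Ki-67 below 10% | None stated | None stated |
| MRI parameters | 95% CI for change | None stated |
| Angiogenesis markers | None stated | ANOVA for a fall from baseline |

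**3. The Mann-Whitney test.** With responders defined by a fall of at least 40%, every responder has a larger percent fall than every nonresponder. Under complete separation the exact two-sided p is 2 / C(n, k) for k responders. At n = 21:
- k = 2: 2/210 = 0.0095
- k = 3: 2/1330 = 0.0015
- k = 4: 2/5985 = 0.0003

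These values depend only on n and k. On absolute change the circularity is nearly complete. In simulations with no drug effect and at least 2 responders, the test was significant in 78%, 83% and 93% of trials at a per-reading CV of 25%, 30% and 40% (assumed baseline median 15%, log-SD 0.6).

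**4. What a 30% share leaves open.** The documents give no reading error, so a log-normal error is assumed. The SD of log(post/pre) is s = sqrt(2 ln(1 + CV²)). If all patients shift alike, a 30% share implies a median change of 0.6 × exp(0.524 s) − 1:

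| CV | s | Median change |
|---|---|---|
| 10% | 0.141 | −35% |
| 20% | 0.280 | −31% |
| 30% | 0.415 | −25% |
| 40% | 0.545 | −20% |

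If instead 30% of patients fall by 60% and the rest do not change (CV 10%), the median m of the log ratio solves 0.3 + 0.7 Φ(m/0.141) = 0.5. So m = −0.080, a median change of −7.7%.

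**5. Which summary to add.** In that mixture the geometric mean ratio is 0.4^0.3 = 0.76, a 24% fall. The Hodges-Lehmann estimate targets about −23%, and its 95% interval covers the true median in only about 88% of trials at n = 21 and 85% at n = 24. It should therefore not be called a median. An order-statistic interval has the right target: 6th to 16th value at n = 21, coverage 1 − 2 P(Bin(21, 0.5) ≤ 5) = 97.3%. For the geometric mean ratio, the 95% limits at n = 21 are the estimate multiplied or divided by 1.20, 1.31, 1.44 or 1.58 for an assumed log-ratio SD of 0.4, 0.6, 0.8 or 1.0.

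**6. Disagreement with the primary test.** In the same mixture:

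| n | Binomial | Signed-rank | Both |
|---|---|---|---|
| 21 | 91% | 53% | 52% |
| 24 (5 or more) | 89% | 61% | 59% |

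**7. The 5% null.** With no drug effect, the chance of an apparent 40% fall is q = Φ(ln 0.6 / s), which equals 5% at a CV of about 22%.

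| CV | q | False success, n = 21 (4 or more) | n = 24 (5 or more) |
|---|---|---|---|
| 20% | 3.4% | 0.5% | 0.1% |
| 25% | 7.1% | 6% | 2.5% |
| 30% | 10.9% | 19% | 11% |
| 40% | 17.4% | 51% | 41% |

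**The case against.** Several points on the other side stand.

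- A responder share with an interval and an exact test is a sound primary analysis, and Section 11.0 states plainly that it is the primary outcome.
- Ki-67 change is not left unanalysed. The planned correlations use the graded fall, although none is a test against no change.
- A reader might infer that Sections 10.1 and 11.0 name rival primary endpoints. They do not: Section 10.1 labels nothing primary. It merely omits the 40% responder.
- The circularity is conditional. Section 10.2 defines histopathological response categories. If those are the responders meant, the Mann-Whitney test is not circular, though it is still not a test against no change.
- The sentence on mean-change intervals names no variable, so a generous reading could stretch it to Ki-67. Its paragraph is about other measures, and one line would settle it.
- A continuous analysis does not isolate the drug effect in a single-arm trial. With an assumed 10% untreated downward shift, CV 20% and n = 21, a signed-rank test is significant in 35% of trials against 6.5% for the binomial test. It is the more exposed of the two.

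A tempting stronger reading is that the 5% null is wrong and the primary test therefore unsafe. Section 2.0, arguing for MRI, does mention "errors due to tissue heterogeneity and use of limited spatial sampling imposed in methods such as histology", but gives no size for them. The false-success figures run from 0.5% to 51% at n = 21 solely according to the CV assumed.

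**Conclusion.** The point holds as a gap in the supportive analysis of the primary marker and as an undefined term. It is not a fault in the primary test, in its power or in Table 1. On the text alone, continuous Ki-67 change has no explicit interval and no test against no change. On the only definition of responder in Section 11.0, the Mann-Whitney p-value for Ki-67 percent change is fixed by the number of responders; this needs no assumption about variability. The range of falls behind a 30% share (medians from about −8% to −35%) does rest on assumed error and response patterns.

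Two inferences are not supported. The documents do not show that 5% is too low, so its missing source is a documentation note only. Nor would an interval for change tell a reader how much of a positive result is due to the drug: without untreated patients, neither analysis can exclude a systematic difference between core biopsy and excision.

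**What to change.** Keep the 40% responder share, its interval, the binomial test and Table 1 as the sole success rule. Then:

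- **Section 11.0, supportive analysis.** Analyse log(post/pre Ki-67) in evaluable patients, adding half a cell to both counts if any count is zero. Report the geometric mean ratio with a 95% interval (paired t on the log scale) and the sample median percent change with an order-statistic 95% interval. If Hodges-Lehmann is used instead, label it a pseudo-median. Any signed-rank test is descriptive and not a condition for success. State that neither analysis can exclude a core-to-excision shift.
- **Mann-Whitney test.** Say which responders are meant. If they are the Ki-67 responders, leave Ki-67 out; otherwise name the Section 10.2 categories.
- **Section 10.1.** List the 40% responder. Report the below-10% share only among patients with baseline Ki-67 of 10% or more, as a description. Even so restricted it shows 4% to 23% with no effect in simulations (assumed baseline median 10–20%, log-SD 0.5–0.7, CV 20–30%).
- **5% null.** Give its source or call it a convention.

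The cost is wording and one analysis of data already collected. Endpoint, success rule, power and accrual are untouched. The downside is that the two results can disagree, as step 6 of the working shows. Requiring both would cut power to 52% at n = 21 in that scenario, so the supportive result must not become a second hurdle, nor its non-significance be read as failure.

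### 24 evaluable, 50% non-evaluability and 42 accrued cannot all be right: 42 gives 21 evaluable, 24 needs 48, and Table 1 itself points to 21

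*Combined protocol and SAP*

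**What the plan says.** All the relevant text is in Section 11.0, Statistical Considerations. A responder is a patient whose Ki-67 falls by at least 40% from baseline. Under the null hypothesis, "no more than 5% of the subjects will exhibit at least 40% decrease in Ki-67 levels".

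Table 1 gives sample sizes for response rates of 0.30 to 0.50 at 80% and 90% power, "using the binomial test with a significance level of 0.05". No sidedness or tail rule is stated for the table.

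The design chosen from it is: "Thus, for 90% power, 24 evaluable subjects are necessary to detect a difference of 25% from the null". Table 1 prints the same 24 at a response rate of 0.30. The section then says: "We anticipate a non-evaluability rate of 50% as quoted by experienced investigators. Hence, we will accrue 42 patients on this trial".

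For the primary analysis it states: "The proportion responding and the 95% confidence interval for this proportion will be calculated". "The 2-sided binomial test with" alpha 0.05 follows, against a null of 0.05. Neither the p-value method nor the interval method is named.

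**The concern.** The accrual target is presented as a consequence of the evaluable number and the non-evaluability rate, but it does not follow from them. No other section gives a second evaluability rate or another derivation of 42. A reader cannot tell whether a trial that ends with 21 evaluable patients has met its target or missed it by three.

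Two things follow. First, one of the three figures is wrong, and it matters which: a wrong 24 costs a wording change, whereas a wrong 42 costs six more patients. Second, whether 24 evaluable patients give 90% power depends on which exact two-sided test is meant, and the plan does not say.

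**Working it through.** **Inputs (all from Section 11.0).** Null rate p0 = 0.05; design alternative p1 = 0.30; alpha 0.05; power 90%; 24 evaluable; 50% non-evaluable; 42 accrued.

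**1. Accrual.**
- Needed for 24 evaluable: 24 / (1 − 0.5) = 48.
- Expected from 42: 42 × (1 − 0.5) = 21, which is 3/24 = 12.5% below 24.
- The common slip 24 × 1.5 gives 36, so it does not explain 42 either.
- For 42 to give 24 on average, non-evaluability would have to be 1 − 24/42 = 42.9%.
- With the evaluable count distributed Binomial(42, 0.5): P(24 or more) = 0.22 and P(21 or more) = 0.56. With 48 accrued, P(24 or more) = 0.56.

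**2. Table 1.** For each n, take the smallest responder count c whose exact test rejects p0 = 0.05; power is P(X ≥ c) for X ~ Binomial(n, p1). Because power rises and falls with n, there are two common choices of n: the smallest that reaches the target, or the one from which power stays at or above it. The exact test can be equal-tailed (upper tail at most 0.025) or minimum-likelihood two-sided; one-sided 0.05 gives the same n as the latter. Entries are n for 80% / 90% power.

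| p1 | Printed | Equal-tailed, smallest n | Min-likelihood, n from which power stays | Equal-tailed, n from which power stays | Min-likelihood, smallest n |
|---|---|---|---|---|---|
| 0.30 | 18 / 24 | 18 / **21** | 18 / **21** | 18 / 25 | 14 / 16 |
| 0.35 | 12 / 18 | 12 / 18 | 12 / 18 | 15 / 18 | 12 / 14 |
| 0.40 | 10 / 12 | 10 / 12 | 10 / 12 | 10 / 15 | 7 / 12 |
| 0.45 | 9 / 10 | 9 / 10 | 9 / 10 | 9 / 10 | 6 / 10 |
| 0.50 | 5 / 9 | 5 / 9 | 5 / 9 | 8 / 9 | 5 / 7 |
| Match | | 9 of 10 | 9 of 10 | 6 of 10 | 4 of 10 |

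Two conventions reproduce every entry except the one used for the design, and both give 21 there. None of the four gives 24. Normal approximations, one- or two-sided, with and without continuity correction, give 15 to 21 for that cell and miss other entries.

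**3. Power at p1 = 0.30.**

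| Evaluable | Equal-tailed: reject at / power | Min-likelihood: reject at / power |
|---|---|---|
| 20 | 4 or more / 89.3% | 4 or more / 89.3% |
| 21 | 4 or more / 91.4% | 4 or more / 91.4% |
| 23 | 5 or more / 86.4% | 4 or more / 94.6% |
| 24 | 5 or more / 88.9% | 4 or more / 95.8% |

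At 21, P(X ≥ 4 | 0.05) = 0.0189, which is below 0.025, so both tests use the same cutoff. At 24 the same tail is 0.0298: above 0.025 but below 0.05, so the cutoffs separate.

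Averaged over the random evaluable count, power is 87.5% (equal-tailed) or 90.7% (minimum-likelihood) with 42 accrued, and 90.8% or 94.3% with 48.

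**4. What the unnamed method changes.**
- Four responders of 24: minimum-likelihood p = 0.030; equal-tailed p = 2 × 0.0298 = 0.060; Clopper-Pearson 95% interval 4.7% to 37.4%, which includes 5%.
- Four responders of 21: p = 0.019 and 0.038; interval 5.4% to 41.9%, which excludes 5%.
- The cutoffs differ at 23 to 28 evaluable (probability 0.31 with 42 accrued). They also differ at 14 to 16 (0.07) and at some counts of negligible probability, about 0.38 in all.

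**The case against.** The best defence is that this is probably a typing slip with little consequence. If 21 was meant, 42 is correct, power at 21 exceeds 90%, and the repair adds no patients. The 78% chance of missing 24 then concerns a number nobody intended; the chance of falling below 21 is 1 − 0.56 = 44%, which is ordinary when accrual is set by expected value. This stands as a limit on the harm. It does not make the printed justification correct, because the reader still has three figures that conflict.

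It is also fair to say that 24 is printed twice, in the text and in the table, and that no software or rule for Table 1 is given. The inference to 21 is therefore strong but not proved, and the claim that only one entry fails holds under two of the four conventions tried. For this reason the sponsor has to confirm the number.

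The unnamed p-value and interval methods are a separate and smaller gap in specification. Correcting the sample-size sentence would not close it, and at exactly 21 evaluable the two exact tests agree. It is raised here because power at 24 cannot be stated without it.

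Finally, the probabilities assume independent evaluability at exactly 50%, which the plan only anticipates. The mismatch between 24, 50% and 42 does not depend on independence.

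**Conclusion.** The concern holds. At 50% non-evaluability, 42 accrued corresponds to 21 evaluable and 24 evaluable corresponds to 48 accrued; the plan's sample-size statement is wrong as written. Table 1 and the accrual figure both point to 21, although the document does not say which number is the slip.

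The statement needs correcting because it is the only justification for the size of the trial, not because power collapses. Under the equal-tailed test, 24 evaluable falls 1.1 points short of 90% (88.9%), and average power with 42 accrued falls 2.5 points short (87.5%). Under the minimum-likelihood test both meet the target (95.8% and 90.7%). These figures assume a true response rate of 0.30; the averages also assume independent evaluability at 50%.

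**What to change.** The sponsor should first confirm which evaluable number was intended.

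- **If 21:** replace 24 with 21 in the Statistical Power paragraph and in Table 1 (0.30, 90% power), and keep accrual at 42. State the rule at 21 evaluable: reject at 4 or more responders, upper-tail size 0.019, power 91.4%. Add that the evaluable count is random, so 91.4% applies at exactly 21, and give the average power for the named test (87.5% equal-tailed, 90.7% minimum-likelihood). Cost: wording and one table cell, with no extra patients.
- **If 24:** either state that 42 accrued is expected to yield only 21, or restate accrual as 48. Give the power at 24 for the named test. Cost: wording alone, or six more patients.

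In both cases, name the exact two-sided p-value, state the convention behind Table 1, and use a confidence interval that agrees with the test: Clopper-Pearson with the equal-tailed test, or the interval obtained by inverting the minimum-likelihood test. This should be settled before the Ki-67 results are seen.

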Specific Aim 1: We hypothesize that a proliferative marker Ki-67 is reduced in patients with preinvasive (DCIS) and very early breast cancer treated with anastrozole. To establish reduction in Ki-67 as a primary surrogate endpoint to breast cancer risk reduction in patients treated with anastrozole we will measure Ki-67 before and after treatment with anastrozole. Consistent with this, it has been demonstrated by Geisler et al that patients with invasive breast cancer show a decrease in Ki-67 on lumpectomy/mastectomy samples when anastrozole is administered for few weeks prior to definitive surgery. In addition, there is a trend for a more profound suppression in those achieving an objective response. Ki-67 will be measured by routine immunohistochemistry.

Specific Aim 2: We hypothesize that histopathological tumor response will be demonstrated in 30-40 percent of patients with preinvasive (DCIS) and early invasive (less than 2 cm) breast cancer treated with anastrozole. The percent ability to reverse early breast cancer lesions in patients treated with anastrozole will be qualified as a secondary surrogate endpoint to breast cancer risk reduction. Consistent with this, it has been demonstrated that 30-40 percent of patients with invasive breast cancer show an infiltration of foamy macrophages and fibrosis on lumpectomy/mastectomy samples when chemotherapy is administered for few months prior to definitive surgery. Further, there is a trend for a more profound change in those achieving a complete clinical response. Importantly, a complete pathological response in these invasive breast cancer has been shown to correlate with improved disease free survival and overall survival in breast cancer patients. A corollary is that if reversibility of early carcinogenic lesions is reliably demonstrated in our present proposal, it would translate into chemoprevention of breast cancer.

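### As written, the Mann-Whitney comparison of responders and nonresponders is circular for Ki-67, because Section 11 defines responders only by their fall in Ki-67 (minor; secondary analysis only)

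*Combined protocol and SAP*

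**What the plan says.** Section 11.0 gives the responder definition twice. In the power paragraph: "Individuals who exhibit at least 40% reduction in Ki-67 from baseline will be categorized as responders". In the primary-outcome paragraph, a patient who reaches the same 40% fall is the one for whom "the participant will be classified as a responder" applies. Neither statement uses any other marker or criterion.

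Between the two stands the analysis at issue: "The comparison of changes in proliferation markers and receptor levels between responders and nonresponders will be performed using the Mann-Whitney U test". It does not redefine the groups or refer to another section.

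The marker that Section 2.0 calls proliferative is Ki-67 (Specific Aim 1: "We hypothesize that a proliferative marker Ki-67 is reduced in patients with preinvasive (DCIS"). No other marker is described that way. The angiogenesis markers, p53 and TSP-1 have their own analysis of variance in Section 11.0.

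A different kind of response appears elsewhere. Objective 1.2 is to "correlate the degree of histopathological response with the degree of Ki-67 response". Section 10.2 sorts histopathological response into CR, PR, SD and PD, and plans to correlate the drop in Ki-67 with the degree of pathological response. It does not use the word responder or divide the four categories into two groups.

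Section 10.1 names the Ki-67 endpoint as "Absolute percent Ki-67 change pre anastrozole and post anastrozole", together with the share of patients below 10%.

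**The concern.** A two-group test is informative when the grouping is set by something other than the variable tested. Here the only grouping that Section 11.0 offers is a threshold on the fall in Ki-67, and the fall in Ki-67 is one of the variables compared. A difference is therefore built in.

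At stake is how the result is read. The trial aims to identify a surrogate endpoint for later prevention studies. A very small p-value for Ki-67 change between responders and nonresponders could be taken as separate evidence of drug effect or of the marker's value, when it mostly restates how many patients crossed the 40% line. The primary analysis already reports that count with a 95% confidence interval and a binomial test.

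**Working it through.** **Inputs from Section 11.0.** Responder: Ki-67 fall of at least 40%. Null proportion 0.05; alternative 0.30; two-sided 0.05. Evaluable patients: 24 as stated, or 42 × (1 − 0.50) = 21 if 42 are accrued and half are not evaluable.

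**The plan's own figure.** For 24 patients, the exact binomial test with upper tail 0.025 rejects at 5 or more responders (tail 0.0060, power 0.889). With the two-sided p-value that orders outcomes by probability it rejects at 4 or more (0.0298, power 0.958). These bracket the stated 90% power. Nothing below disputes that figure.

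**Percent change.** Every responder is at −40% or lower and every nonresponder is above −40%, so the groups never overlap. The k responders hold the k lowest ranks, one of C(n,k) equally likely arrangements under the test's null. Doubling for two sides gives p = 2/C(n,k), ignoring tied values.

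| k | n = 21 | n = 24 |
|---|---|---|
| 1 | 2/21 = 0.095 | 2/24 = 0.083 |
| 2 | 2/210 = 0.0095 | 2/276 = 0.0072 |
| 7 | 2/116280 = 0.000017 | 2/346104 = 0.0000058 |

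The p-value is below 0.05 whenever each group has at least two patients. From the binomial distribution:

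- With a 5% response probability this happens with probability 0.283 (n = 21) or 0.339 (n = 24). There is no responder, so no test, with probability 0.341 or 0.292.
- With a 30% response probability it happens with probability 0.994 or 0.998.

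These are probabilities that the groups are large enough, not error rates. The groups differ by definition.

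**Absolute change.** Section 10.1 can be read as change in percentage points, and the groups can then overlap. As an illustration, a fall from 50% to 35% is 15 points but only a 30% reduction (nonresponder), while a fall from 10% to 5% is 5 points and a 50% reduction (responder). The documents give no baseline or variability figures, so the following are assumptions: log-normal baseline with median 15% and log-SD 0.7 (range 0.5 to 0.9), and normal log ratios with SD ln(0.6)/z(0.05) = −0.511/−1.645 = 0.311, the value at which 5% respond by chance when the mean log ratio is 0. Trials without responders count as not significant.

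- No drug effect: p < 0.05 in about 17% of simulated trials at n = 21 (15–21% over the baseline range) and about 23% at n = 24 (19–26%).
- 30% responders (mean log ratio −0.511 + 0.311 × 0.524 = −0.348): about 65% at n = 21 and 73% at n = 24 with log-SD 0.7. In 4,000 simulated trials per setting, the range over log-SD 0.9 to 0.5 was about 52–80% and 61–87%.

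The link to the grouping is looser than on percent change, but it remains.

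**A marker unrelated to Ki-67.** With the same groups, n = 24 and at least three patients per group, a simulated independent marker reached p < 0.05 in 3.9% to 5.5% of runs. The receptor half of the sentence is therefore a legitimate test.

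**The case against.** **The authors may have meant histopathological responders.** There is support for this. Objective 1.2 links Ki-67 to pathology, and Specific Aim 1 cites earlier work in which "there is a trend for a more profound suppression in those achieving an objective response". That comparison would not be circular. But Section 11.0 does not say it, does not refer to Section 10.2, and surrounds the sentence with Ki-67 definitions. An analyst working from the text would use the Ki-67 groups. The intention is open, and the need for a clarifying sentence stands.

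**Nothing depends on this test.** This is right and sets the severity. The primary analysis is the binomial test with its interval, and the comparison enters no decision rule.

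**The 2/C(n,k) result may be on the wrong scale.** It holds for percent change only. On absolute change the p-value does not depend on the responder count alone, and every figure for that scale rests on assumed values.

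**Stronger readings the documents do not support.** A reader might infer that the test has an inflated Type I error. It does not: patients grouped by Ki-67 fall truly differ in Ki-67 fall, so no true null is being wrongly rejected. The fault is that the answer is known in advance. A reader might also infer that Objective 1.2 would be analysed on the wrong patients. Section 10.2 already plans a degree-with-degree correlation for it, which needs no responder split and does not use the Mann-Whitney sentence.

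**Conclusion.** The point holds as a minor fault in a stated secondary analysis. Read as written, the Ki-67 part of the Mann-Whitney comparison is circular. On percent change this follows from the definition without further assumptions: the exact p-value is 2/C(n,k), for example 0.0072 with 2 responders and 0.0000058 with 7 among 24. On absolute change the circularity is partial, and its size depends on assumed baseline spread and variability. In either case the p-value adds essentially nothing to the primary result.

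The ER and PgR comparison, the primary binomial test, the sample size and the Section 10.2 correlation serving Objective 1.2 are unaffected. The conclusion rests on taking Section 11.0's own definition of responder as the one that applies. If histopathological responders were intended, the circularity disappears, but the grouping still has to be stated.

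**What to change.** Amend the sentence in Section 11.0 in one of two ways.

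- If Ki-67 responders are meant: remove Ki-67 from the Mann-Whitney comparison and keep it for ER and PgR.
- If histopathological responders are meant: say so and state how the Section 10.2 categories are split, for example CR and PR against SD and PD. Note that this overlaps the correlation already planned there.

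This costs one or two sentences and no new data.

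An optional addition is to report the Section 10.1 pre/post Ki-67 change in all evaluable patients with a 95% confidence interval from one prespecified paired method, such as the Hodges-Lehmann interval that goes with the Wilcoxon signed-rank test. Section 11.0 already plans intervals for mean change in the MRI parameters, whereas Ki-67 levels are summarised by arithmetic means and the change is analysed only as responder or not. No further hypothesis test is needed. The downside is one small extra analysis, and in a single-arm trial its interval cannot separate a drug effect from differences between core-biopsy and surgical specimens.
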